#### Other medical conditions

- [23] Have clinically significant ECG abnormalities including QTc, Fridericia's correction >450 msec for males and >470 msec for females.
- [24] Have a history of additional risk factors for Torsades de Pointes such as, heart failure, hypokalemia, or a family history of long QT syndrome.

[25] Have clinically relevant abnormal blood pressure or heart rate as determined by the investigator.

- [26] Have an unstable or uncontrolled illness, including but not limited to a cerebrocardiovascular, respiratory, hepatic, renal, gastrointestinal, endocrine, hematologic, or neurologic disease, or abnormal laboratory values at screening, that in the opinion of the investigator would potentially affect participant safety within the study or interfere with the interpretation of data.
- [27] Have a diagnosis or history of malignant disease within 5 years prior to baseline, with the following exceptions:
  - a. Basal cell or squamous epithelial carcinomas of the skin that have been resected with no evidence of metastatic disease for 3 years.
  - b. Cervical carcinoma in situ, with no evidence of recurrence within 5 years prior to baseline.
- [28] Have a history of or current significant psychiatric disorders.
- [29] Are, in the judgment of the investigator, actively suicidal and therefore deemed a significant risk for suicide.

- [31] Have a history of major surgery within 12 weeks prior to screening or will require major surgery during the study.
- [32] Have a history of significant allergies to lidocaine or other topical anesthetics used during skin biopsy.

#### **Vaccines**

- [33] Have received any live vaccine (that is, live attenuated) within less than 4 weeks before randomization, or intend to receive a live vaccine during the study, or within 4 weeks after receiving the last dose of study intervention.
  - **Note:** The following are not considered live vaccines: RNA vaccines, vaccines with inactive viral elements, and/or nonreplicating viral vector vaccines.
- [34] Have received a Bacillus Calmette-Guerin vaccine or treatment within less than 4 weeks before randomization or intend to during the study and within less than 5 half-lives after the last dose of intervention.

#### **Prior/concomitant therapy**

[35] Have received any investigational intervention within 4 weeks or 5 half-lives prior to screening, whichever is longer.

[36] Have a history of any disease that required treatment with oral or parenteral corticosteroids for more than 2 weeks within 24 weeks prior to screening.

- [37] Have received biologic treatments for immune conditions, such as monoclonal antibodies, including marketed or investigational drugs, within 12 weeks or 5 half-lives prior to baseline, whichever is longer.
- [38] Have received systemic nonbiologic treatment for immune conditions within 4 weeks prior to baseline (see Section 10.11.2).
- [39] Have received topical psoriasis treatment within 14 days prior to baseline (see Section 10.11.2).
- [40] Are unable or unwilling to avoid excessive sun exposure or use of tanning booths for at least 4 weeks prior to baseline and during the study.
- [41] Are currently using or plan to use medications that prolong the QT/QTc interval.

## Prior/concurrent clinical study experience

[42] Are currently enrolled in any other clinical study involving an investigational product or any other type of medical research judged not to be scientifically or medically compatible with this study.

#### Other exclusions

- [43] Have evidence of current, or history within 1 year prior to screening, of any substance use disorder(s) of any severity as defined by the DSM-V in the opinion of the investigator, excepting disorders of nicotine or caffeine use.
- [44] Have donated blood of more than 500 mL within 4 weeks prior to screening.
- [45] Have received blood products within 6 months prior to screening.
- [46] Exclusion Criterion [46] has been deleted.
- [47] Are Lilly employees or are employees of any third party involved in the study who require exclusion of their employees.
- [48] Are investigator site personnel directly affiliated with this study and/or their immediate families. Immediate family is defined as a spouse, parent, child, or sibling, whether biological or legally adopted.
- [49] Are unsuitable for inclusion in this study in the opinion of the investigator or the sponsor.

# **5.3.** Lifestyle Considerations

#### **Blood donation**

Participants should not donate blood during participation in the study.

#### Sperm donation and contraception

See Appendix 4, Section 10.4.2.

#### **Prohibited medications and procedures**

See Section 10.11.2 for prohibited medications and procedures.

#### **5.4.** Screen Failures

A screen failure occurs when a participant who consents to participate in the clinical study is not subsequently randomly assigned to study intervention. A minimal set of screen failure information is required to ensure transparent reporting of screen failure participants to meet the CONSORT publishing requirements and to respond to queries from regulatory authorities. Minimal information includes demography, screen failure details, and any SAE.

Individuals who do not meet the criteria for participation in this study (screen failure) may be rescreened 1 time and require a new identification number. Repeating of laboratory tests during the screening period does not constitute rescreening. See Section 8.2.8 and Appendix 7, Section 10.7 for retesting for TB.

# 5.5. Criteria for Temporarily Delaying Enrollment of a Participant

This section is not applicable for this study.

[figure not shown]
# 6. Study Intervention(s) and Concomitant Therapy

Study intervention is defined as any investigational intervention(s), marketed product(s), placebo, or medical device(s) intended to be administered to/used by a study participant according to the study protocol.

# 6.1. Study Intervention(s) Administered

As stated in the SoA, study intervention will be self-administered by participants at home except for the visits specified in the SoA.

This table lists the interventions used in this clinical study.

Abbreviations: EU = European Union; CC

# Packaging and labeling

Study interventions will be supplied by the sponsor or its designee in accordance with current Good Manufacturing Practice. Study interventions will be labeled as appropriate for country requirements.

# 6.2. Preparation, Handling, Storage, and Accountability

The investigator or designee must confirm appropriate storage conditions have been maintained during transit for all study intervention received and any discrepancies are reported and resolved before use of the study intervention.

Only participants enrolled in the study may receive study intervention. Only authorized study personnel may supply study intervention.

At the study site, all study intervention must be stored in a secure, environmentally controlled, and monitored (manual or automated) area in accordance with the labeled storage conditions with access limited to the investigator and authorized study personnel. For off-site (at-home) administration, sponsor will provide storage instructions.

The investigator or authorized study personnel are responsible for study intervention accountability, reconciliation, and record maintenance, that is, receipt, reconciliation, and final disposition records.

Further guidance and information for the final disposition of unused study interventions are provided in the Pharmacy Manual.

# 6.3. Assignment to Study Intervention

The IWRS will allocate newly enrolling participants to groups according to the randomization ratios. For randomization ratios, see Section 4.1.

Participants will be stratified at baseline by prior exposure to biologic therapy for psoriasis (biologic naïve vs. biologic experienced).

# 6.4. Blinding

This is a double-blind study. Blinding will be maintained throughout the conduct of the study, as described in the separate Blinding and Unblinding Plan.

Investigators will remain blinded to each participant's assigned study intervention within each dose group, throughout the course of the study.

# **Emergency unblinding**

The IWRS will be programmed with blind-breaking instructions. In case of an emergency, the investigator has the sole responsibility for determining if unblinding of a participants' intervention assignment is warranted. Participant safety must always be the first consideration in making such a determination. If a participant's intervention assignment is unblinded, the sponsor must be notified immediately after breaking the blind.

#### Discontinuation from the study in case of unblinding

If an investigator, site personnel performing assessments, or participant is unblinded, the participant must be discontinued from the study (Section 7.2). In cases where there are ethical reasons to have the participant remain in the study, the investigator must obtain specific approval from the sponsor's medical monitor for the participant to continue in the study.

# **6.5.** Study Intervention Compliance

Participant compliance with study intervention will be assessed at each applicable visit during the treatment period by counting returned capsules per bottle.

A participant will be considered significantly noncompliant if he or she misses more than 20% of the prescribed doses of study intervention during the study, unless the participant's study intervention is withheld by the investigator for safety reasons. Similarly, a participant will be considered significantly noncompliant if he or she is judged by the investigator to have taken 20% more than the prescribed amount of medication during the study.

Participants will be counseled by study staff on the importance of taking the study intervention as prescribed, as appropriate.

A record of the number of capsules dispensed to and returned by each participant must be maintained and reconciled with study intervention and compliance records. Intervention start and stop dates, including dates for intervention interruptions will also be recorded in the CRF.

Participant compliance will be further defined in the SAP.

#### 6.6. Dose Modification

Dose modifications will not be allowed during this study.

# 6.7. Continued Access to Study Intervention after the End of the Study

Study intervention will not be available to participants after completion of the study.

#### **6.8.** Treatment of Overdose

The sponsor does not recommend specific treatment for an overdose.

In the event of an overdose, the investigator should:

- Contact the medical monitor immediately.
- Evaluate the participant to determine, in consultation with the medical monitor, whether study intervention should be interrupted or whether the dose should be reduced.
- Closely monitor the participant for any AE/SAE and laboratory abnormalities as medically appropriate.
- Obtain a plasma sample for PK analysis if requested.

# 6.9. Prior and Concomitant Therapy

See Appendix 11, Section 10.11 for lists of medications that are permitted or prohibited in this study.

Any medication or vaccine, including over-the-counter or prescription medicines, vitamins, and/or herbal supplements, that the participant is receiving at the time of enrollment or receives during the study must be recorded.

All participants should maintain their usual medication regimens for concomitant conditions or diseases throughout the study, unless those medications are specifically excluded in the protocol.

Participants taking concomitant medications should be on stable dosages at the time of baseline and should remain at stable dosages throughout the study, unless changes need to be made because of AEs.

Participants should consult with authorized site personnel before taking any new medications or supplements during the study. Authorized site personnel should consult the sponsor's medical monitor if there are any questions about concomitant therapies during the study.

Participants who require treatment with concomitant medications that are prohibited in this study will be permanently discontinued from the study intervention (Section 7.1.3).

# 7. Discontinuation of Study Intervention and Participant Discontinuation/Withdrawal

This section describes reasons for a participant's

- temporary or permanent discontinuation of study intervention (Section 7.1), or
- discontinuation (withdrawal) from the study (Section 7.2).

# 7.1. Discontinuation of Study Intervention

# 7.1.1. Liver Chemistry Stopping Criteria

Interrupting study intervention based on liver test elevations in participants with normal or near-normal baseline liver tests

In study participants with normal or near normal baseline liver tests (ALT, AST, ALP <1.5x ULN), the study intervention should be **interrupted** and close hepatic monitoring initiated (see Section 8.2.11) if 1 or more of these conditions occur:

Elevation	Exception	
ALT or AST >8x ULN		
ALT or AST >5x ULN for more than 2 weeks		
ALT or AST >3x ULN and either TBL >2x ULN or INR >1.5	For participants with Gilbert's syndrome: If baseline direct bilirubin is >0.5 mg/dL,	
	then doubling of direct bilirubin should be	
	used for drug interruption decisions rather	
	than TBL >2x ULN.	
ALT or AST $>3x$ ULN with the appearance of fatigue, nausea,		
vomiting, right upper quadrant pain or tenderness, fever, rash,		
and/or eosinophilia (>5%)		
ALP >3x ULN, when the source of increased ALP is the liver		
ALP >2.5x ULN and TBL >2x ULN	For participants with Gilbert's syndrome:	
	If baseline direct bilirubin is >0.5 mg/dL,	
	then doubling of direct bilirubin should be	
	used for drug interruption decisions rather	
	than TBL >2x ULN.	
ALP >2.5x ULN with the appearance of fatigue, nausea,		
vomiting, right upper quadrant pain or tenderness, fever, rash,		
and/or eosinophilia (>5%)		
Source: FDA 2009 and other consensus guidelines, with minor modifications		

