# Interrupting study intervention based on elevated liver tests in participants with abnormal baseline liver tests

In study participants with abnormal baseline liver tests (ALT, AST, ALP  $\geq$ 1.5x ULN), the study intervention should be **interrupted** if 1 or more of these conditions occur:

Elevation	Exception	
ALT or AST >4x baseline		
ALT or AST $>3x$ baseline for more than 2 weeks		
ALT or AST >2x baseline and either TBL >2x ULN or INR >1.5	For participants with Gilbert's syndrome: If baseline direct bilirubin is >0.5 mg/dL, then doubling of direct bilirubin should be used for drug interruption decisions rather than TBL >2x ULN.	
ALT or AST >2x baseline with the appearance of fatigue, nausea, vomiting, right upper quadrant pain or tenderness, fever, rash, and/or eosinophilia (>5%)  ALP >2.5x baseline, when the source of increased ALP is the		
liver		
ALP >2x baseline and TBL >2x ULN	For participants with Gilbert's syndrome: If baseline direct bilirubin is >0.5 mg/dL, then doubling of direct bilirubin should be used for drug interruption decisions rather than TBL >2x ULN.	
ALP $>$ 2x baseline with the appearance of fatigue, nausea,		
vomiting, right upper quadrant pain or tenderness, fever, rash, and/or eosinophilia (>5%)		
Source: FDA 2009 and other consensus guidelines, with minor modifications		

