## **8.2.11.** Hepatic Safety Monitoring

# Close hepatic monitoring

Laboratory tests (Appendix 6, Section 10.6), including ALT, AST, ALP, TBL, direct bilirubin, GGT, and creatine kinase, should be repeated within 48 to 72 hours to confirm the abnormality and to determine if it is increasing or decreasing, if 1 or more of these conditions occur:

If a participant with baseline results of	develops the following elevations:
ALT or AST <1.5x ULN	ALT or AST ≥2x ULN
ALP <1.5x ULN	ALP ≥2x ULN
TBL <1.5x ULN	TBL ≥2x ULN (except for participants with Gilbert's syndrome)
ALT or AST ≥1.5x ULN	ALT or AST ≥2x baseline
ALP≥1.5x ULN	ALP ≥2x baseline
TBL ≥1.5x ULN	TBL ≥1.5x baseline (except for participants with Gilbert's syndrome)

If the abnormality persists or worsens, clinical and laboratory monitoring, and evaluation for possible causes of abnormal liver tests should be initiated by the investigator in consultation with the Lilly-designated medical monitor. At a minimum, this evaluation should include physical examination and a thorough medical history, including symptoms, recent illnesses (for example, heart failure, systemic infection, hypotension, or seizures), recent travel, history of concomitant

medications (including over-the-counter), herbal and dietary supplements, history of alcohol drinking and other substance abuse.

Initially, monitoring of symptoms and hepatic biochemical tests should be done at a frequency of 1 to 3 times weekly, based on the participant's clinical condition and hepatic biochemical tests. Subsequently, the frequency of monitoring may be lowered to once every 1 to 2 weeks, if the participant's clinical condition and laboratory results stabilize. Monitoring of ALT, AST, ALP, and TBL should continue until levels normalize or return to approximate baseline levels.

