#### Comprehensive hepatic evaluation

A comprehensive evaluation should be performed to search for possible causes of liver injury if 1 or more of these conditions occur:

If a participant with baseline results of	develops the following elevations:	
ALT or AST <1.5x ULN	ALT or AST ≥2x ULN with hepatic signs/symptoms a , or	
	ALT or AST ≥5x ULN	
ALP <1.5x ULN	ALP ≥3x ULN	
TBL <1.5x ULN	TBL ≥2x ULN (except for participants with Gilbert's syndrome)	
ALT or AST ≥1.5x ULN	ALT or AST ≥2x baseline with hepatic signs/symptoms a , or	
	ALT or AST ≥3x baseline	
ALP ≥1.5x ULN	ALP ≥2x baseline	
TBL ≥1.5x ULN	TBL $\geq$ 2x baseline (except for participants with Gilbert's syndrome)	

<sup>a Hepatic signs/symptoms are severe fatigue, nausea, vomiting, right upper quadrant abdominal pain, fever, rash, and/or eosinophilia >5%.

At a minimum, this evaluation should include physical examination and a thorough medical history, as outlined above, as well as tests for prothrombin time INR; tests for viral hepatitis A, B, C, or E; tests for autoimmune hepatitis; and an abdominal imaging study (for example, ultrasound or CT scan).

Based on the patient's history and initial results, further testing should be considered in consultation with the Lilly-designated medical monitor, including tests for hepatitis D virus, cytomegalovirus, Epstein-Barr virus, acetaminophen levels, acetaminophen protein adducts, urine toxicology screen, Wilson's disease, blood alcohol levels, urinary ethyl glucuronide, and blood phosphatidylethanol. Based on the circumstances and the investigator's assessment of the participant's clinical condition, the investigator should consider referring the participant for a hepatologist or gastroenterologist consultation, magnetic resonance cholangiopancreatography, endoscopic retrograde cholangiopancreatography, cardiac echocardiogram, or a liver biopsy.

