# Allowance for additional laboratory testing

Additional tests may be performed at any time during the study as determined necessary by the investigator or required by local regulations.

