# 10.6. Appendix 6: Liver Safety: Suggested Actions and Follow-up Assessments

# Hepatic evaluation testing

See Section 8.2.11 for guidance on appropriate test selection.

The Lilly-designated central laboratory should complete the analysis of all selected testing except for testing listed in the investigator-designated local laboratory table. The central laboratory will report results if a validated test or calculation is available.

Local testing may be performed *in addition to central testing* when necessary for immediate participant management.

The local laboratory must be qualified in accordance with applicable local regulations.

Tests assayed by Lilly-designated central laboratory		
Hepatic Hematology Panel	Hepatitis A virus (HAV) testing:	
Hemoglobin	HAV total antibody	
Hematocrit	HAV IgM antibody	
Erythrocytes (RBCs - red blood cells)	Hepatitis B virus (HBV) testing:	
Leukocytes (WBCs - white blood cells)	Hepatitis B surface antigen (HBsAg)	
Differential:	Hepatitis B surface antibody (anti-HBs)	
Neutrophils, segmented	Hepatitis B core total antibody (anti-HBc)	
Lymphocytes	Hepatitis B core IgM antibody	
Monocytes	HBV DNAb	
Basophils	Hepatitis C virus (HCV) testing:	
Eosinophils	HCV antibody	
Platelets	HCV RNAb	
Cell morphology (RBC and WBC)	Hepatitis D virus (HDV) testing:	
Hepatic Clinical Chemistry Panel	HDV antibody	
Total bilirubin	HDV IgM antibody	
Direct bilirubin	Hepatitis E virus (HEV) testing:	
Alkaline phosphatase (ALP)	HEV IgG antibody	
Alanine aminotransferase (ALT)	HEV IgM antibody	
Aspartate aminotransferase (AST)	HEV RNAb	
Gamma-glutamyl transferase (GGT)	Anti-nuclear antibody (ANA)	
Creatine kinase (CK)	Anti-smooth muscle antibody (ASMA) a	
Hepatic Coagulation Panel	Anti-actin antibody c	
Prothrombin time, INR (PT-INR)	Immunoglobulin IgA (quantitative)	
Urine Chemistry	Immunoglobulin IgG (quantitative)	
Drug screen	Immunoglobulin IgM (quantitative)	
Haptoglobin		

Tests assayed ONLY by investigator-designated local laboratory		
Acetaminophen	Cytomegalovirus (CMV) testing:	
Acetaminophen protein adducts	CMV antibody	
Alkaline phosphatase isoenzymes	CMV DNAb	
Ceruloplasmin	Herpes simplex virus (HSV) testing:	
Copper	HSV (Type 1 and 2) antibody	
Ethyl alcohol (EtOH)	HSV (Type 1 and 2) DNA b	
Phosphatidylethanol (PEth)	Liver kidney microsomal type 1 (LKM-1) antibody	
Urine Chemistry	Microbiology Culture:	
Ethyl glucuronide (EtG)	Blood	
Epstein-Barr virus (EBV) testing:	Urine	
EBV antibody		

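### The liver stopping rule uses INR once ALT or AST passes 3x ULN (2x baseline if abnormal), but below 5x ULN (3x baseline), without symptoms or an ALP or bilirubin trigger, no legible text expressly requires an INR

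*Protocol*

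**What the plan says.** Protocol 7.1.1 has two interruption tables. With normal or near-normal baseline liver tests, one criterion is "ALT or AST >3x ULN and either TBL >2x ULN or INR >1.5". With abnormal baseline tests, the counterpart is "ALT or AST >2x baseline and either TBL >2x ULN or INR >1.5". In both, INR is an alternative to bilirubin, so either alone is enough once the enzyme threshold is passed.

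An INR result could come from these places:

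- **Routine laboratory tests.** No legible row of the Schedule of Activities (1.3) or panel in Appendix 2 (10.2) contains a coagulation test. Total bilirubin is in the clinical chemistry panel.
- **Close hepatic monitoring (8.2.11).** This starts at ALT or AST of at least 2x ULN, or at least 2x baseline if baseline is abnormal. The text reads "Laboratory tests (Appendix 6, Section 10.6), including ALT, AST, ALP, TBL, direct bilirubin, GGT, and creatine kinase, should be repeated" within 48 to 72 hours. For later follow-up, "Monitoring of ALT, AST, ALP, and TBL should continue until levels normalize or return to approximate baseline levels".
- **Comprehensive hepatic evaluation (8.2.11).** The minimum content is examination and history, "as well as tests for prothrombin time INR", viral and autoimmune hepatitis tests, and abdominal imaging.
- **Appendix 6 (10.6).** PT-INR is listed in the central Hepatic Coagulation Panel, but the appendix opens with "See Section 8.2.11 for guidance on appropriate test selection".
- **Investigator discretion (Appendix 2).** "Additional tests may be performed at any time during the study as determined necessary by the investigator".

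SAP 4.7.4.2 refers to 8.2.11 for additional tests and lists any coagulation data obtained. It adds no INR requirement.

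**The concern.** A stopping criterion can be applied only if its inputs are measured. The bilirubin limb is always available because bilirubin is drawn routinely. The INR limb is there for a different case, impaired synthetic function without raised bilirubin, so the bilirubin limb cannot stand in for it.

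The close-monitoring list names GGT and creatine kinase, neither of which is a 7.1.1 criterion, and leaves out INR, which is. A site that follows the list exactly could keep dosing a participant who meets a stated interruption criterion, because nobody looked.

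The consequence for the individual is large. Under 7.1.1, an interrupted participant may resume only after consultation with the medical monitor, and only if liver tests return to baseline and a self-limited cause other than study drug is found. Otherwise treatment is discontinued. This is the first study of the compound in psoriasis patients, earlier human safety data come from healthy adults (2.3.3), and the risk-management text in 2.3.1 relies on 7.1.1 and 8.2.11.

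**Working it through.** The plan gives no figure to reproduce. The check sets the interruption thresholds in 7.1.1 against the triggers in 8.2.11.

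| | Normal or near-normal baseline | Abnormal ALT/AST baseline |
|---|---|---|
| Close monitoring starts (INR not named) | ALT/AST ≥2x ULN | ≥2x baseline |
| INR interruption arm opens | >3x ULN | >2x baseline |
| Comprehensive evaluation on ALT/AST alone (INR called for) | ≥5x ULN | ≥3x baseline |
| Comprehensive evaluation on ALT/AST with symptoms | ≥2x ULN | ≥2x baseline |
| Interruption on ALT/AST alone, over 2 weeks | >5x ULN | >3x baseline |
| Interruption on ALT/AST alone, at once | >8x ULN | >4x baseline |

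The comprehensive evaluation is also triggered by ALP ≥3x ULN or bilirubin ≥2x ULN or, where that analyte's own baseline is abnormal, by ≥2x baseline.

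**Setting.** Take INR above 1.5, bilirubin and ALP normal, none of the listed symptoms, and an elevation that has not yet lasted more than 2 weeks. Count in steps of 0.1x.

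*Normal baseline*
- INR is the only possible interruption trigger from 3.1x to 8.0x ULN: (8.0 − 3.1)/0.1 + 1 = 50 steps.
- No express INR requirement from 3.1x to 4.9x: (4.9 − 3.1)/0.1 + 1 = 19 steps.
- INR called for from 5.0x to 8.0x: 50 − 19 = 31 steps.

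*Abnormal baseline*
- INR is the only possible trigger from 2.1x to 4.0x baseline: (4.0 − 2.1)/0.1 + 1 = 20 steps.
- No express requirement from 2.1x to 2.9x: (2.9 − 2.1)/0.1 + 1 = 9 steps.
- INR called for from 3.0x to 4.0x: 20 − 9 = 11 steps.

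These counts describe the rules, not how often participants would fall there.

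**Duration.** The 2-week condition matters only above the gap. The duration-based criteria need >5x ULN or >3x baseline, so they never apply inside the gap, however long the elevation lasts.

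**The abnormal-baseline gap in ULN units.** The gap runs from 2 × baseline to 3 × baseline. The legible text does not show the entry laboratory limits, so the baselines are assumed:

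- 1.5x ULN: 3.0x to 4.5x ULN
- 2.0x ULN: 4.0x to 6.0x ULN
- 2.5x ULN: 5.0x to 7.5x ULN

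**Is a sample already being taken?** Yes. Both gaps lie above the close-monitoring threshold, so a repeat draw within 48 to 72 hours is due throughout.

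**The case against.** The strongest reply is that INR is already within close monitoring. The 8.2.11 list is introduced as non-exhaustive, it cites Appendix 6, and Appendix 6 contains PT-INR. Since 7.1.1 makes INR a condition, a careful investigator would order one. On that reading this is a drafting point. What stands is that INR is permitted and a good site would probably obtain it. But Appendix 6 is a menu that also holds hepatitis serology and immunoglobulins, so citing it cannot mean that every test is repeated, and it sends test selection back to 8.2.11. The cross-references end at a list without INR. The protocol names INR where it wants it, in the comprehensive evaluation, so a site could reasonably take its absence elsewhere as not required.

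Other points carry some weight:

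- **Wording.** The verb is *should* for interruption, repeat testing and comprehensive evaluation alike. The real contrast is between a test that is named and one that is not.
- **Oversight.** A persistent or worsening abnormality brings in the medical monitor and further laboratory monitoring, initially 1 to 3 times weekly. That makes an INR more likely, but the stated minimum at that point is examination and history.
- **Narrowness.** Symptoms, eosinophilia above 5%, a bilirubin or ALP trigger, or a higher enzyme level each bring INR in.
- **Abnormal baselines.** Section 2.3.1 says significant liver abnormalities are excluded, so this half may apply to few people. The protocol still provides a separate table for them. The 2x and 2.5x examples are illustrations only.
- **Redaction.** Some Schedule of Activities and Appendix 2 rows are hidden, and the laboratory manual is not available. A hidden INR requirement cannot be fully excluded. The close-monitoring text, where the test is needed, is legible.

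**Conclusion.** The concern holds. The INR arm opens at >3x ULN (>2x baseline), but the first express call for INR on enzymes alone is at 5x ULN (3x baseline). Between those points, without listed symptoms or an ALP or bilirubin trigger, applying a stated safety stopping rule depends on a discretionary test. From 5x to 8x ULN in the first 2 weeks, and from 3x to 4x baseline, INR is called for and the arm works as written.

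The number affected is expected to be small, and the documents give no rate. Efficacy analyses are untouched. The conclusion rests on the legible text of 7.1.1, 8.2.11, the Schedule of Activities and Appendices 2 and 6. It is a mismatch between a safety rule and the tests that feed it, and it should be corrected because correction is cheap.

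**What to change.** In the close hepatic monitoring text of 8.2.11, add PT-INR to the 48 to 72 hour repeat tests and to subsequent monitoring whenever ALT or AST is >3x ULN (normal or near-normal baseline) or >2x baseline (abnormal baseline). The interruption rule then has its input across its whole stated range.

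The cost is a one-line protocol clarification and one added central-laboratory assay, already in Appendix 6, on a draw that is taking place anyway, in a small number of participants.
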